**6.2.3 Point of enrollment**

Subjects will be considered enrolled in the study when they have:  
Been informed of all aspects of the study and have signed Informed Consent document

- Acknowledged the appropriate patient data release information (included in the Informed Consent document)
- Satisfied the Inclusion/Exclusion Criteria
- Implanted with an approved or cleared Wright Medical product included in this study

Investigators should document subject enrollment by completing the enrollment logs located within the site's trial master file. The Source documentation should clearly state that all inclusion and exclusion criteria have been met and the patient data release and informed consent documents have been signed and appropriately dated prior to any study related activity.

The investigative sites will be assigned three-digit a site code \*\*\*, and at enrollment the subject will be assigned a sequential subject identification number corresponding to the order the subject was enrolled (i.e. the first subject enrolled at each site will be site number \*\*\* followed by subject identifier 001). The assigned codes will be used to identify the subject on all case report forms. All investigative sites will be provided protocol training during the site initiation visits.

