## 6.2 Subjects

### 6.2.1 Eligibility Criteria (Inclusion/Exclusion)

#### 6.2.1.1 Inclusion Criteria

Subjects to be included in the study must meet all of the following criteria:

- Willing and able to consent to participate (written, informed consent);
- Willing and able to attend/complete the requested follow-up visits;
- Considered for treatment with one or more approved or cleared Wright Medical products included in this study.

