#### 6.3.5.2 Procedure Visit

The information related to the subject's operation will be collected and recorded according to the Operative Information Case Report Forms. The following operative information related to the primary procedure will be documented on these forms:

- Indication
- Procedure
- Any previous surgery to index procedure
- Date of operation
- Site location
- Op report uploaded with patient identifiers removed
- Intraoperative complications (to be collected on the Adverse Event Case Report Form)
- Product description, product code, lot number for each Wright Product component implanted
- Any additional Wright Product (not included in the study) that was used in the procedure

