### **7.3 Data Analysis**

Improvements in subject quality of life after surgery will be assessed by constructing 95% confidence interval for the mean change from baseline score in EQ-5D-5L and FAMM total and component scores.

|   |  |  |
|---|--|--|
|  | Clinical Investigation Plan
Foot and Ankle Products | CIP- INT19-MDR-001
Version: 2 |
|---|--|--|

Survivorship of a Wright product will be assessed based on adverse event resulting from the presence or performance of the device. The Kaplan Meier survivorship method and life table analysis will be employed. Time to adverse event due to the presence or performance of the implant will be the survivorship endpoint for each Wright device. Also, time to reoperation to exchange or remove any part of the Wright device due to failure of the implant will also determine the Wright product survivorship. Subjects who will not experience these events will be censored at the last follow-up visit. The Kaplan Meier survival curve and the 95% Confidence Interval will be constructed.

Safety endpoints will include all adverse events (AE), serious AE (SAE), unanticipated adverse device effects (UADEs).

All subjects enrolled in the study will be assessed for safety. Adverse events and other safety evaluations will be reported as frequency and rates as appropriate, cumulative over the different follow-up schedules.

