**11.3 Adverse Event Assessment**

The subjects will be assessed for adverse events at the operative visit and post-operatively. The site will be given an adverse event case report form to complete. The information collected on the assessment will include the following:

- Date of event or onset
- Procedure related
- Device related
- Narrative of adverse event
- Treatment required
- SAE
- Subject withdrawal
- Hospitalization
- Adverse event outcome

- Mode of sponsor notification
- Date of resolution

The data provided on the adverse event case report form will be queried to assess as whether they were unanticipated and for severity. These will be reported accordingly

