### 5. Population and Progress

All analysis will include all subjects implanted with any of the Wright devices listed in Appendix 1, hence called Treated population.

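### Enrolment and every analysis set require implantation, so a consented patient who leaves surgery with no study device after a failed attempt is in no safety result

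*Protocol*

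**What the plan says.** Protocol 6.2.1.1 admits patients on intention: "Considered for treatment with one or more approved or cleared Wright Medical products included in this study". Protocol 6.3.5.1 has history, demographics, EQ-5D-5L and FAAM collected before surgery.

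Protocol 6.2.3 is narrower. Besides consent, data release and eligibility, a subject counts as enrolled only when "Implanted with an approved or cleared Wright Medical product included in this study". The subject number is issued at enrolment and identifies the subject on all case report forms.

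The analysis sets follow from that:

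- Protocol 7.3: "All subjects enrolled in the study will be assessed for safety".
- SAP 5: "All analysis will include all subjects implanted with any of the Wright devices listed in Appendix 1, hence called Treated population". No separate safety set is defined.

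Both documents nevertheless treat the operation as part of the safety record. Protocol 11.3 states: "The subjects will be assessed for adverse events at the operative visit and post-operatively". Protocol 6.3.5.2 sends intra-operative complications to the adverse-event form. For study devices, the same section asks for "Product description, product code, lot number for each Wright Product component implanted". It also asks for Wright products outside the study that were used in the procedure.

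SAP 3.1 counts a patient's data towards each device received. SAP 6.6 makes device-failure rates the basis of the survival rates. SAP 6.1 describes patient accounting by device implanted or used, which is wider than SAP 5.

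**The concern.** The study exists to show the safety and performance of each device, and Protocol 7.1 requires separate analyses by device. A component that breaks or will not seat during surgery is the earliest failure a device can have. Protocol 11.2 defines device-related events by the presence or performance of the device, so such an event qualifies. If a patient enters the safety results only when a study device ends up implanted, inclusion depends partly on the outcome being measured. SAP 4.1 also describes a consecutive series of eligible subjects at each site, and a condition met only during surgery breaks that series after eligibility.

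Device groups are small. SAP 3.1 reports 122 patients in total, with many devices listed, and summarises any device implanted in at least 10. At that size one missing case changes the reported rate visibly.

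**Working it through.** **Plan's own figure.** The documents give no rate of failed or abandoned implantation, so there is nothing to reproduce on this point. The EQ-5D sample size (1.960 × 0.313 / 0.1)² = 37.63, rounded up to 38, reproduces and is unaffected.

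**Who is counted.** Take a consented, eligible patient in whom study device A is tried and abandoned.

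| Outcome of surgery | Enrolled (Protocol 6.2.3) | Protocol 7.3 safety | SAP 5 Treated | Device A result |
|---|---|---|---|---|
| Second unit of A implanted | Yes | Yes | Yes | In A's denominator; event can be recorded |
| Different study device B implanted | Yes | Yes | Yes | Event can be recorded; no product or lot field for A and no denominator entry for A |
| No study device implanted | No | No | No | Absent from numerator and denominator |

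The third row is full exclusion. The second is a gap in attribution only: the narrative or the uploaded operative report may name A, but no structured field or analysis rule uses that.

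**Direction.** Let a device have N implanted subjects, x recorded failures and k omitted failed attempts. The reported rate is x/N and the rate per attempt is (x + k)/(N + k). The difference is

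(x + k)/(N + k) − x/N = k(N − x) / [N(N + k)],

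which is never negative. Omitting a failure can only lower the rate.

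**Illustration.** k is an assumption. Each omitted case is taken to be one device failure in a patient who left with no study device. Exact (Clopper–Pearson) upper 95% limits are in brackets.

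| Implanted, recorded failures | k = 0 | k = 1 | k = 2 |
|---|---|---|---|
| 10, none (SAP 3.1 reporting minimum) | 0/10 = 0% (30.8%) | 1/11 = 9.1% (41.3%) | 2/12 = 16.7% (48.4%) |
| 40, none (original plan, not met) | 0/40 = 0% (8.8%) | 1/41 = 2.4% (12.9%) | 2/42 = 4.8% (16.2%) |

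An attempt abandoned for a reason unrelated to the device, such as sizing, would add to the denominator alone. With one recorded failure among 10, one such attempt moves 1/10 = 10.0% to 1/11 = 9.1%. The one-way direction therefore concerns omitted failures, not every omitted attempt.

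**The case against.** The strongest reply is that the plan chose its target: the stated objective is safety and performance after implantation, and an implanted set matches it. That stands for EQ-5D, FAAM and post-operative survivorship. It does not answer the point for safety, because the plan itself collects intra-operative complications and assesses adverse events at the operative visit, then has no analysis set for some of the patients concerned.

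Second, much capture is already planned: the adverse-event form records device-relatedness, a narrative and treatment; the operative report is uploaded; the sponsor reviews each event. This stands for any patient who received some study device. A reader might infer that every patient whose attempted device was not left in place is excluded. The documents do not support that: a second unit or another study product keeps the patient in the safety set.

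Third, *implanted* is undefined. A device placed and removed in the same operation might count, with Protocol 6.2.2 then discontinuing the subject. This stands, and is a reason to define the term. Likewise, a reader might infer that a non-implanted patient has no subject number for an adverse-event form. Protocol 6.2.3 read literally says so, but baseline forms are completed before surgery, so the text conflicts with itself and does not settle the matter.

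Fourth, no such case may have occurred, and an abandoned attempt need not be a device failure. Both stand. The documents support *could be under-counted*, not *were*.

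Fifth, enrolment stopped on November 1, 2021, before the SAP took effect on 12 January 2022. Changing the enrolment point or the operative form cannot recover past data, and rewording SAP 5 alone may add nobody. This limits what the fix can achieve for the existing cohort.

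**Conclusion.** The point holds in a bounded form. A consented, eligible patient in whom a study device was attempted, and who left surgery with no study device, is outside the protocol's safety population and every SAP analysis. Where a different study device was implanted, the patient and the event are included, but the abandoned device has no product or lot field and no denominator under its own name.

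Per-device failure and device-related event rates could therefore be too low, since an omitted failure cannot make them too high. The amount cannot be estimated from the documents. The shift from 0/10 to 1/11 (9.1%) assumes one omitted case that was a true device failure; with no such case the results are unchanged. The conclusion rests on reading *implanted* as left in place at the end of surgery. The change is worth making because it is cheap and removes a selection that depends on the outcome.

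**What to change.** **Analysis sets.** In SAP 5 and Protocol 7.3, define the safety set as consented, eligible subjects in whom implantation of a study device was attempted. Count an intra-operative device failure as an event at time zero in the adverse-event and device-failure tables, under the device attempted. Keep the implanted set for EQ-5D, FAAM and post-operative survivorship. Amend SAP 6.6 to say that survival rates use post-operative failures among implanted subjects, so that the two counts are not mixed.

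**Wording.** Define *implanted*. Reconcile Protocol 6.2.3, Protocol 7.3, SAP 5 and the wider description in SAP 6.1. Resolve the conflict between issuing the subject number after implantation and completing baseline forms before surgery.

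**Existing cohort.** Protocol 8.1 requires sites to retain signed consents and source documents. Use them to report, by device, how many subjects were consented but not implanted, with reasons. Where records do not allow this, state the restriction to implanted subjects as a limitation beside the safety tables.

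**Any further enrolment.** Assign the subject number at consent plus eligibility, and record product and lot for components attempted as well as implanted.

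**Cost.** A small records check, definition changes, one operative-form field if enrolment resumes, and ethics approval of the protocol amendment (Protocol 8.3). There are no added visits. A few extra subjects would appear in patient accounting, and failure rates may look slightly less favourable.

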**6.2.4 Total expected duration of the clinical investigation**

The total study duration from, first patient, first visit, (FPFV) to last patient, last visit (LPLV) could potentially be up to 15 years. The sites will send the EQ5D-5L, FAAM and Patient Survey to consented and enrolled patients for completion. The site will input information into the electronic data capture (EDC) system. If survey indicates there was an adverse event associated with the Wright Medical product, the site will make every attempt to reach the subject and complete an adverse event assessment form.

**6.2.5 Expected duration of each subject's participation**

Based on varied definitions of product clinical lifetime, the follow-up period will be 12 weeks to 10 years

**6.2.6 Number of Subjects required to be included in the CI**

We will prospectively collect EQ-5D-5L for subjects enrolled in this study. Because the devices are utilized in a variety of skeletal anatomic locations within the foot and ankle, a literature search was conducted to better understand the EQ-5D outcomes for various orthopedic procedures. Hasson et al. (Hasson et al. Spine. 33(25): 2819-2830, 2008) reported on EQ-5D outcomes from various procedures, including arthrodesis of the ankle or subtalar joints. The sample size calculation is based on precision of estimate from the post-operative EQ-5D:  $0.549 \pm 0.313$  (mean  $\pm$  SD). Using the standard deviation (0.313), a sample size was calculated:

|            |                              |                            |        |      |
|------------|------------------------------|----------------------------|--------|------|
| Alpha=0.05 | Half width (precision) = 0.1 | Standard deviation = 0.313 | Side=2 | n=38 |
|------------|------------------------------|----------------------------|--------|------|

Based on this calculation, a minimum sample size for each device: n = 40 or until sufficient data is collected to satisfy the notified bodies.

**6.2.7 Estimated enrollment time**

The enrollment period will be 5 years

**6.3 Procedure**

**6.3.1 Clinical Investigation Summary**

Overview of all the clinical investigation related procedures that subjects undergo during the clinical investigation.

**6.3.2 Screening**

Subjects with interest in participating in the study, after signing the informed consent document, will then be invited to participate if they meet the Inclusion Criteria.

**6.3.3 Informed Consent**

Prior to conducting any protocol required data collection, including evaluations and questionnaires, written informed consent must be obtained

from the subject in compliance with 21 CFR Part 50 or if required the 2005 Mental Capacity Act.

Subjects will be recruited based on interest in participating in the study. All subjects will be consented by an appropriately trained clinician or research staff using the IRB/EC/REC approved consent form in order to participate in the study and prior to any data collection, or any study procedure. The study clinician or research staff will assess whether the subject can give informed consent or not during the consent process. The potential participant must be allowed ample time to review the informed consent and should be allowed to take the time to read, review, ask questions, and receive answers as well as being fully informed of all aspects of the study before a decision is made to participate.

**6.3.4 Schedule of Visits and Assessment Requirements**

Subjects will be seen pre-operatively, at the operative visit and prospectively at the Final Clinical Follow-Up visit required as determined by the physician as the last standard of care visit for the procedure performed.

Additionally, PROMS and safety may be followed yearly to sufficiently assess the safety of the product over the clinical lifetime as needed based on the current risk analysis for the product.

**6.3.5 Procedures and Patient Assessments**

**6.3.5.1 Baseline Visit**

The subject will be assessed for eligibility and given time to review and sign the informed consent. Once the subject has signed the informed consent, the subject's medical history and demographic information will be collected and recorded onto the demographic case report form. The following information will be collected on these forms:

- Month and Year of birth
- Gender
- Height
- Weight
- BMI calculation
- Smoking status
- Race
- Concomitant health conditions (diabetes and other medical conditions, etc.)

The subjects will be given the patient reported outcome measures (PROM) to complete. The measures include:

- EQ-5D-5L is a generic health survey that can be used to compare improvement across different interventions and measure changes in health-related quality of life over time.
- Foot and Ankle Ability Measure (FAAM) is a PROM designed to be a comprehensive assessment of physical performance amongst individuals with a range of leg, foot and ankle disorders. Unlike many PROMs, FAAM is not a disease-specific measure but is instead region-specific

#### 6.3.5.2 Procedure Visit

The information related to the subject's operation will be collected and recorded according to the Operative Information Case Report Forms. The following operative information related to the primary procedure will be documented on these forms:

- Indication
- Procedure
- Any previous surgery to index procedure
- Date of operation
- Site location
- Op report uploaded with patient identifiers removed
- Intraoperative complications (to be collected on the Adverse Event Case Report Form)
- Product description, product code, lot number for each Wright Product component implanted
- Any additional Wright Product (not included in the study) that was used in the procedure

#### 6.3.5.3 Follow-up Visits

Subjects will be seen prospectively at the Final Clinical Follow-Up visit required as determined by the physician as standard of care for the procedure performed. At this visit the subject will be given the EQ-5D and the FAAM to complete. The subject will also be assessed for any adverse events. The data provided on the adverse event case report form will be queried to assess as whether they were unanticipated and for severity. These will be reported accordingly. The surgeon will be given The Surgeon Survey with Radiographic Assessment to complete at this visit. The following information will be collected from the survey:

- Imaging available
- Performance of Wright product
- Fusion/Consolidation time for applicable products

PROMs and safety may be followed yearly to sufficiently assess the safety of the product over the clinical lifetime as needed based on the current risk analysis for the product. If a subject's product meets this requirement, the subject will be followed yearly until the requirement is met. At those visits, the site will send the subject the EQ-5D and FAAM to complete as well as the Patient Survey to assess safety. The survey will collect the following data:

- Complications
- Device removal

#### **6.3.5.4 Clinical Investigations Exit**

Individual subject enrollment will be considered complete once the subject has completed all of their study visits required by the study protocol.

#### **6.4 Clinical Investigation Monitoring**

The study will be monitored by Wright Medical or its authorized representatives in accordance with the internal procedures of Wright Medical. The frequency of the visits (on-site or remote) will be determined by Wright. This may vary based on the enrollment and data collected at the sites, any compliance concerns and need for additional training and oversight.

Upon study commencement, regular on-site or remote monitoring visits will be conducted to ensure:

- ongoing compliance with the study protocol;
- ongoing compliance with any conditions of approval of the reviewing IRB/EC/REC;
- maintenance of complete study and regulatory records
- continued acceptability of the site's facilities

Source documents and Investigator site files will be reviewed during the monitoring visits, including, but is not limited to:

- reviewing electronic case report forms for accuracy and completeness;
- verifying timely and accurate data collection (in comparison with the source documentation);
- reviewing and resolving missing or inconsistent study data;
- verifying the investigational site maintains all required source documents, supporting medical records, and signed Informed Consent Documents; and
- verifying the investigational site maintains documentation and reports for any AEs

Monitors will evaluate and summarize the results of each visit in a written report that identifies any repeated data problems and providing specific recommendations for the resolution of noted deficiencies.

## **7.0 Statistical Considerations**

### **7.1 Study design**

This study is a global, multi-center, post-market observational study to demonstrate the safety and performance of the Wright products listed in Section 3.3. Data will be collected at baseline, surgery, at the last scheduled standard of care and/or surgeon release follow-up (FU) time point. The subjects improvement in post-surgical quality of life will be assessed using EQ-5D-5L and Foot and Ankle Ability Measure (FAAM).

An adverse event resulting from the presence or performance of the device and removal due to implant failure will determine the survivorship of the Wright product. Further, safety will be assessed by subject experience of device complication and adverse events during the study period.

All effectiveness and safety analysis will be performed separately for each Wright Medical device included in the study.

### **7.2 Sample Size**

We will prospectively collect EQ-5D-5L for subjects enrolled in this study. Because the devices are utilized in a variety of skeletal anatomic locations within the foot and ankle, a literature search was conducted to better understand the EQ-5D outcomes for various orthopedic procedures. Hasson et al. (Hasson et al. Spine. 33(25): 2819-2830, 2008) reported on EQ-5D outcomes from various procedures, including arthrodesis of the ankle or subtalar joints. The sample size calculation is based on precision of estimate from the post-operative EQ-5D:  $0.549 \pm 0.313$  (mean  $\pm$  SD). Using the standard deviation (0.313), a sample size was calculated:

|              |                              |                            |          |        |
|--------------|------------------------------|----------------------------|----------|--------|
| Alpha = 0.05 | Half width (precision) = 0.1 | Standard deviation = 0.313 | Side = 2 | n = 38 |
|--------------|------------------------------|----------------------------|----------|--------|

Based on this calculation, a minimum sample size for each device: n = 40 or until sufficient data is collected to satisfy the notified bodies.

